#### 5.5 Treatments

#### 5.5.1 Treatments Administered

Rovalpituzumab tesirine, the investigational agent under study in this protocol, is an ADC. All subjects randomized will receive premedication consisting of dexamethasone/placebo orally (PO) at 8 mg twice daily on Day –1, Day 1 (the day of dosing), and Day 2 of each cycle in which rovalpituzumab tesirine/placebo is administered. Dexamethasone/placebo dosing should occur such that there are approximately 12-hours (i.e., 10 – 14 hours) between AM and PM doses. The first dose of the dexamethasone/placebo on the day of dosing should be at least 30 minutes but no more than 4 hours prior to the rovalpituzumab tesirine/placebo infusion. If the dose of dexamethasone/placebo is vomited within 15 minutes of taking the medication, the subject should retake the medication.

In the event that a subject arrives for rovalpituzumab tesirine/placebo administration on Day 1, but has not taken any or all required dexamethasone/placebo doses on Day –1 and/or Day 1, rovalpituzumab tesirine/placebo administration may not proceed, and rovalpituzumab tesirine/placebo will be held until the required dexamethasone/placebo dosing has occurred.

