## 5.5.4 Selection and Timing of Dose for Each Subject

### 5.5.4.1 Dosing

Dosing is based on actual body weight of the subject to the nearest kilogram, assessed in the clinic prior to dosing at each cycle, and administered according to the calculated dose. In cases of weight gain due to fluid retention, dosing should be based on most recent prefluid retention actual weight.

[figure not shown]
Subjects must meet all of the following criteria on each dosing day before receiving blinded investigational product:

- Absolute neutrophil count (ANC)  $\geq 1,000/\mu L$
- Platelet count  $\geq 75,000/\mu L$
- Resolution of blinded investigational product-related AEs, including findings indicative of pleural or pericardial effusions, and clinically-significant laboratory abnormalities to Grade 0 or 1 (excluding ANC and alopecia), or to baseline grade.

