Safety Set will comprise all subjects who receive at least one dose of study drug and subjects will be classified according to treatment received. Thus a subject who is randomized to the rovalpituzumab tesirine arm but does not receive rovalpituzumab tesirine will be considered in the placebo arm for safety analysis. Dexamethasone treatment will not be taken into consideration for subjects' classification in the Safety set.

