6.5 Definition of Study Days and Rx Days

Study Day of any observation is defined for post-randomization observations as:

$$\text{Study Day} = \text{Date of observation} - \text{Date of randomization} + 1,$$

and for observations pre-dating randomization as:

$$\text{Study Day} = \text{Date of observation} - \text{Date of randomization}.$$

Thus, the day of randomization is defined as Study Day 1, while the day prior to the randomization is defined as Study Day –1 (there is no Study Day 0).

Study Rx Day of any post-baseline observation is defined as the number of days from the day of the first dose of any study drug (rovalpituzumab tesirine, Dexamethasone, matching placebo) to the date of observation. It is calculated for each post-treatment observation as follows:

$$\text{Study Rx Day} = \text{Date of observation} - \text{Date of first dose of any study drug} + 1$$

Definition of Analysis Windows

During the treatment period, all time points and corresponding time windows are based on Study Rx Days, unless specified otherwise. For longitudinal analyses, especially for the laboratory data (hematology, chemistry, and urinalysis), the time windows specified below describe how data collected at protocol specified visits will be assigned to. If more than one observation is included in a time window, the observation closest to the nominal day should be used. If there are two observations equally distant to the nominal day, the later one will be used in analyses.

Table 1. Visit Window for Laboratory[#], Vital Sign Assessments and Physical Examination

Study Visit (Week) [*]	Nominal Study Rx Day	Time Window (Study Rx Days Range)
Baseline	1	≤ 1
3	22	2 to ≤ 32
6	43	33 to ≤ 53
9	64	54 to ≤ 74
12	85	75 to ≤ 106
18	127	107 to ≤ 137
21	148	138 to ≤ 158
24	169	159 to ≤ 179
27	190	180 to ≤ 200
30	211	201 to ≤ 232
...
...
18•X	7•18•X + 1	7•18•X - 19 to ≤ 7•18•X + 11
18•X + 3	7•(18•X + 3) + 1	7•18•X + 12 to ≤ 7•(18•X + 3) + 11
18•X + 6	7•(18•X + 6) + 1	7•(18•X + 3) + 12 to ≤ 7•(18•X + 6) + 11
18•X + 9	7•(18•X + 9) + 1	7•(18•X + 6) + 12 to ≤ 7•(18•X + 9) + 11
18•X + 12	7•(18•X + 12) + 1	7•(18•X + 9) + 12 to ≤ 7•(18•X + 12) + 22
...

laboratory tests include hematology, serum chemistry and urinalysis.

* Every third cycle (6-week cycle) treatment will be omitted.

Table 2. Visit Window for Coagulations Tests and Patient Reported Outcomes (PRO)

Study Visit (Week)*	Nominal Study Rx Day	Time Window (Study Rx Days Range)
Baseline	1	≤ 1
6	43	2 to ≤ 64
12	85	65 to ≤ 106

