11.0 Safety Analysis

11.1 General Considerations

Unless otherwise specified, safety analyses will be performed on the Safety Set. No statistical comparisons will be performed between arms. No p-values and CIs will be provided.

Unless specified, all summaries/analyses involving AEs will only include treatment-emergent adverse events (TEAEs). TEAEs are defined as any adverse event with onset or increase severity after the first dose of study drug (rovalpituzumab tesirine or matching placebo; dexamethasone or matching placebo) and no more than 70 days after the last dose of study drug administration. AEs where the onset date is the same as the study drug start date are assumed to be treatment-emergent, unless the study drug start time and the AE start time are collected and the AE start time is prior to the study drug start time. If an incomplete onset date was collected for an AE, the AE will be assumed to be treatment-emergent unless there is evidence that confirms that the AE was not treatment-emergent (e.g., the AE end date was prior to the date of the first dose of study drug).

Adverse events will be coded and summarized by system organ class and preferred term (and severity) according to the Medical Dictionary for Regulatory Activities (MedDRA) version 21.0 or higher. The table of clinical toxicity grades modified from the National Cancer Institute Common Terminology Criteria for Adverse Events (NCI CTCAE) version 4.0 will be used in the grading of adverse events and laboratory abnormalities that are reported as adverse events.

Summary of continuous safety endpoints (e.g., change from baseline values in laboratory values, vital signs parameters) will include the mean, standard deviation, median and range. In the context of change from baseline analyses, summary of baseline and post-baseline data will also be provided. Categorical safety endpoints (e.g., incidence of AEs or clinically significant ECG values) will be summarized using frequencies and percentages. All the analyses will be carried out by treatment group.

Unscheduled assessment will not be included in the summary of change from baseline, but will be included in producing shift tables and summary of lab abnormalities.

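### Subjects randomized to Rova-T who took only the premedication capsules count as placebo in the Safety Set, so the placebo column holds every never-infused subject and the Rova-T column none

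*SAP*

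**What the plan says.** SAP 5.0 sets both entry and classification: "Safety Set will comprise all subjects who receive at least one dose of study drug and subjects will be classified according to treatment received". It then states that a subject randomized to Rova-T "but does not receive rovalpituzumab tesirine will be considered in the placebo arm for safety analysis", and adds: "Dexamethasone treatment will not be taken into consideration for subjects' classification in the Safety set". Protocol 8.1 has the same rule, so the two documents do not conflict.

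SAP 5.0 does not define study drug. Other SAP sections use a broad meaning:

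- SAP 11.1 counts an adverse event as treatment-emergent by its onset or worsening "after the first dose of study drug (rovalpituzumab tesirine or matching placebo; dexamethasone or matching placebo").
- SAP 6.5 counts Study Rx Days from the "first dose of any study drug (rovalpituzumab tesirine, Dexamethasone, matching placebo").
- SAP 11.2 also names dexamethasone as study drug when it describes related events.

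On timing, protocol 5.5.1 says "All subjects randomized will receive premedication consisting of dexamethasone/placebo orally (PO) at 8 mg twice daily on Day" −1, Day 1 and Day 2. The infusion follows on Day 1 and is conditional. Protocol 5.5.4.1 says: "Subjects must meet all of the following criteria on each dosing day before receiving blinded investigational product". Protocol 5.5.1 holds the infusion if capsules were missed, and protocol 5.5.4.2.2 delays it if an adverse event prevents full capsule dosing.

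**The concern.** The capsules come first and the infusion is conditional, so a subject can take a capsule and never be infused. On the SAP's broad meaning of study drug, that subject is in the Safety Set. The classification sentence turns on not having received Rova-T, rather than on having received placebo. A capsule-only subject from the Rova-T arm is therefore shown as placebo without any placebo infusion.

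The rule works in one direction only. Capsule-only placebo subjects stay where they were randomized, and no capsule-only subject can appear under Rova-T. If missing the infusion goes with poor condition, early adverse events and fatal events in these subjects fall on the placebo column, and Rova-T looks safer by comparison. Attribution is also blurred: an event judged related to the capsules in a Rova-T-randomized subject would be tabulated under placebo.

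**Working it through.** The plan states no expected number of never-infused subjects and no Safety Set size, so there is no planned figure to reproduce. The check has two parts.

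**1. Following the rule for each kind of subject (broad meaning of study drug)**

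| Randomized to | Received | In Safety Set? | Column |
|---|---|---|---|
| Rova-T | Rova-T infusion | Yes | Rova-T |
| Rova-T | Capsules only | Yes | Placebo |
| Rova-T | Placebo infusion in error | Yes | Placebo |
| Placebo | Placebo infusion | Yes | Placebo |
| Placebo | Capsules only | Yes | Placebo |
| Either | Nothing | No | None |

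Row 2 is the defect. Row 3 is ordinary as-treated classification and is correct.

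**2. Size, for illustration**

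Inputs from the documents: 740 subjects randomized 1:1 (SAP 4.3 and 4.4), so n = 740/2 = 370 per arm.

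Assumptions, none of them in the documents:

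- k capsule-only subjects per arm, at 1–2% of 370. 1% is 3.7, taken as 4; 2% is 7.4, taken as 7.
- Event rate b = 10% in infused subjects of both arms, so there is no true difference.
- Event rate s = 30% to 60% in never-infused subjects.
- Every other randomized subject is infused as assigned.

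Under the rule as written:

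- Rova-T column: n − k subjects, all infused, rate b.
- Placebo column: n + k subjects, of whom n − k were infused and 2k never infused. Rate = [(n − k)b + 2ks]/(n + k).
- Artificial gap = placebo rate − b = 2k(s − b)/(n + k).

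| k | s | Rova-T column | Placebo column | Gap (points) |
|---|---|---|---|---|
| 4 | 30% | 10.0% of 366 | (36.6 + 2.4)/374 = 10.43% | 0.43 |
| 4 | 60% | 10.0% of 366 | (36.6 + 4.8)/374 = 11.07% | 1.07 |
| 7 | 30% | 10.0% of 363 | (36.3 + 4.2)/377 = 10.74% | 0.74 |
| 7 | 60% | 10.0% of 363 | (36.3 + 8.4)/377 = 11.86% | 1.86 |
| 4 or 7 | 10% | 10.0% | 10.0% | 0 |

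The gap is about 0.4–1.9 points over this range, and zero when s = b.

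If the set is limited to infused subjects in both arms, both columns have n − k subjects at rate b and the gap is zero. Keeping capsule-only subjects in their randomized arm also gives zero, because each column then has rate [(n − k)b + ks]/n.

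**The case against.** **Study drug could mean the infusion alone.** The protocol synopsis names only Rova-T as study drug, and SAP 9.0 uses the term for the Day 1 infusion. On that reading capsule-only subjects never enter the set, and the disputed sentence covers only a Rova-T subject given placebo in error, who is classified correctly. This stands as evidence of inconsistent use. It does not remove the problem, because the SAP's explicit definitions are the broad ones and the sentence does not require a placebo infusion.

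**Two stronger readings are tempting but unsupported.** A reader might infer that the rule moves the sickest never-infused subjects of both arms into placebo. Only Rova-T-randomized subjects change column. Nothing in the documents says that they are sicker:

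- The neutrophil and platelet limits for dosing repeat the eligibility limits, and randomization is at most 3 days before Cycle 1 Day 1.
- The criterion on resolved drug-related events has little to act on before the first infusion.
- Withdrawal or logistics could also explain a missed infusion.

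The provision for an adverse event that prevents capsule dosing makes higher risk plausible, but it describes a delay, not a cancellation.

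A reader might also put the distortion at 2–4 points. With the right denominators, 8/374 = 2.1% and 14/377 = 3.7%. Those figures need every such subject to have the event and ignore the background rate, so they are worst cases on assumed counts.

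**The consequences are limited.** This also stands. SAP 11.1 plans no between-arm tests, p-values or confidence intervals for safety. Deaths are compared by randomized arm through OS. Disposition is summarized by arm (protocol 8.1.1), and serious and fatal events are listed (SAP 11.4).

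**As-treated logic says not to charge events to a drug that was never given.** That is right for the Rova-T column, but it does not justify charging them to a placebo infusion that was never given either.

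**Conclusion.** The concern holds on the SAP's own broad use of study drug. Capsule-only subjects randomized to Rova-T are counted as placebo, and all never-infused subjects in the Safety Set sit in one column. The asymmetry follows from the text alone. A bias in favor of Rova-T follows only if these subjects are at higher risk, which is plausible but not shown.

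The range of about 0.4–1.9 points rests entirely on the assumed counts and event rates above. No hypothesis test or type I error is affected. The documents imply through the blinded pairing, but do not state outright, that capsules in the Rova-T arm are active dexamethasone; the misclassification does not depend on it. This is a modest, one-directional flaw in tables that readers will compare directly, and it is worth correcting before unblinding.

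**What to change.** In SAP 5.0 and protocol 8.1:

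- Define the Safety Set as subjects with at least one infusion of Rova-T or its placebo.
- Classify a subject as Rova-T if any Rova-T was infused, and as placebo only if placebo alone was infused.
- Keep the statement that capsules do not determine the arm, and say that capsules alone do not qualify a subject for the set.
- List capsule-only subjects and their adverse events separately by randomized arm, with the count per arm.

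The broad definitions in SAP 6.5 and 11.1 can stay, so that events after the first capsule still count for infused subjects. The separate listing keeps capsule-only events visible, since this change takes them out of the main adverse event tables.

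The cost is a sentence or so in each document, one short listing and a slightly smaller Safety Set.

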6.0 Analysis Conventions

This section provides general considerations for data handling, summary, and analysis.

Continuous variables will be summarized by sample size (N), mean, standard deviation (St. Dev.), median, minimum, and maximum. Frequency and percentage will be provided for categorical variables and 95% confidence intervals (CIs) will be generated for parameter estimates of interest, unless specified otherwise.

6.1 Dealing with Multiple Values on the Same Day

In cases where multiple values are collected on the same day at baseline or post-baseline visit, either the arithmetic average (e.g., for continuous summary) or worst value (e.g., for shift tables) will be used for further analyses.

6.2 Definition of Baseline

Unless otherwise specified, the baseline observation is defined as the last non-missing measurement collected prior to or on the first dose date of blinded investigational product (rovalpituzumab tesirine or matching placebo; dexamethasone or matching placebo).

6.3 Definition of Final Observation

For lab and vital sign parameters, the final observation is defined as the last non-missing post-baseline measurement collected not more than 70 days after the last dose of study drug.

6.4 Missing Data

No missing data imputation will be implemented, unless specified otherwise.

6.5 Definition of Study Days and Rx Days

Study Day of any observation is defined for post-randomization observations as:

$$\text{Study Day} = \text{Date of observation} - \text{Date of randomization} + 1,$$

and for observations pre-dating randomization as:

$$\text{Study Day} = \text{Date of observation} - \text{Date of randomization}.$$

Thus, the day of randomization is defined as Study Day 1, while the day prior to the randomization is defined as Study Day –1 (there is no Study Day 0).

Study Rx Day of any post-baseline observation is defined as the number of days from the day of the first dose of any study drug (rovalpituzumab tesirine, Dexamethasone, matching placebo) to the date of observation. It is calculated for each post-treatment observation as follows:

$$\text{Study Rx Day} = \text{Date of observation} - \text{Date of first dose of any study drug} + 1$$

Definition of Analysis Windows

During the treatment period, all time points and corresponding time windows are based on Study Rx Days, unless specified otherwise. For longitudinal analyses, especially for the laboratory data (hematology, chemistry, and urinalysis), the time windows specified below describe how data collected at protocol specified visits will be assigned to. If more than one observation is included in a time window, the observation closest to the nominal day should be used. If there are two observations equally distant to the nominal day, the later one will be used in analyses.

Table 1. Visit Window for Laboratory[#], Vital Sign Assessments and Physical Examination

Study Visit (Week) [*]	Nominal Study Rx Day	Time Window (Study Rx Days Range)
Baseline	1	≤ 1
3	22	2 to ≤ 32
6	43	33 to ≤ 53
9	64	54 to ≤ 74
12	85	75 to ≤ 106
18	127	107 to ≤ 137
21	148	138 to ≤ 158
24	169	159 to ≤ 179
27	190	180 to ≤ 200
30	211	201 to ≤ 232
...
...
18•X	7•18•X + 1	7•18•X - 19 to ≤ 7•18•X + 11
18•X + 3	7•(18•X + 3) + 1	7•18•X + 12 to ≤ 7•(18•X + 3) + 11
18•X + 6	7•(18•X + 6) + 1	7•(18•X + 3) + 12 to ≤ 7•(18•X + 6) + 11
18•X + 9	7•(18•X + 9) + 1	7•(18•X + 6) + 12 to ≤ 7•(18•X + 9) + 11
18•X + 12	7•(18•X + 12) + 1	7•(18•X + 9) + 12 to ≤ 7•(18•X + 12) + 22
...

laboratory tests include hematology, serum chemistry and urinalysis.

* Every third cycle (6-week cycle) treatment will be omitted.

Table 2. Visit Window for Coagulations Tests and Patient Reported Outcomes (PRO)

Study Visit (Week)*	Nominal Study Rx Day	Time Window (Study Rx Days Range)
Baseline	1	≤ 1
6	43	2 to ≤ 64
12	85	65 to ≤ 106
18	127	107 to ≤ 148
24	169	149 to ≤ 190
30	211	191 to ≤ 232
...
...
6•X	7•6•X + 1	7•6•X + 1 - 20 to ≤ 7•6•X + 1 + 21
...

* Every third cycle (6-week cycle) treatment will be omitted.
Coagulation tests are performed at screening visit, first day of each cycle, and end of treatment visit.

7.0 Demographics, Baseline Characteristics, Medical History, Previous/Concomitant Medications, and Prior Oncology Therapies

Data for demographic, baseline characteristics, medical/surgical history, previous/concomitant medications and prior oncological procedures will be summarized for each treatment arm and overall on both the DLL3^{high} Set and Randomized Set.

7.1 Demographic and Baseline Characteristics

The following demographic, current disease history and baseline disease characteristics (including stratification variables) will be summarized by treatment groups.

Demographic variable	Baseline disease characteristics

 • Age • Weight • Sex • Race (White, Black or African American, Asian, American Indian or Alaskan Native, Native Hawaiian or Pacific Islander) • Ethnicity (Hispanic or Latino, Not Hispanic or Latino, Other) • Age 
 ○ < 40, 40 - < 65, ≥ 65 yr • History of tobacco product use and alcohol use (current, former, never, unknown) • Region of the world (North America, Asia, Europe, Rest of the world) 	
 • TNM staging at the start of the FL treatment • RECIST v1.1 response after completion of first line platinum-based therapy at screening assessment (SD, CR/PR) • History of CNS metastases (Yes, No) • PCI status (PCI, No PCI, NA) • DLL3 expression level (unknown, < 25%, 25% - < 75%, ≥ 75%) • ECOG performance score • LDH: ≤ ULN vs. > ULN
	
Baseline disease status
 
 • Time from initial diagnosis to start of randomization • Time from most recent prior cancer therapy (as defined by C4D1 in the frontline platinum therapy) to randomization • Number of metastatic sites, 0 – 1 vs. > 1

Continuous data (e.g., age, height, and weight) will be summarized with N, mean, standard deviation (St. Dev.), median, minimum, and maximum. Frequencies and percentages will be computed for the categorical variables.

There will be no statistical comparison for demographic and baseline measurements.

7.2 Medical History

Medical history data will be summarized and presented using conditions/diagnoses as captured on the eCRF. The conditions/diagnoses will be presented in alphabetical order. The number and percentage of subjects with a particular condition/diagnosis will be summarized for each treatment arm. Subjects reporting more than one condition/diagnosis will be counted only once for that condition/diagnosis. There will be no statistical comparison for the medical history between treatment arms.

7.3 Prior and Concomitant Medications

A prior medication is defined as any medication with start date prior to the date of randomization and collected on the electronic case report forms (eCRFs). A concomitant medication is defined as any drug that taken on the day of or after randomization, but not 70 days after the last study drug administration (rovalpituzumab tesirine or matching placebo; dexamethasone or matching placebo) regardless of the start and stop date. Medications taken on the day of the first dose of study drug are counted as concomitant medications.

For reporting purpose, the following conservative approach will be followed for determination of prior and concomitant medication:

Start date	End date	
Prior to Study Day 1	Prior to Study Day 1	Prior medication
Missing	Prior to Study Day 1	Prior medication
Prior to Study Day 1	Study Day 1 to Last dose + 70 day	Both prior medication and concomitant medication
Study Day 1 to Last dose + 70 day	Study Day 1 to Last dose + 70 day	Concomitant medication
Missing	Study Day 1 to Last dose + 70 day	Concomitant medication
Study Day 1 to Last dose + 70 day	Missing	Concomitant medication
Missing	Missing	Concomitant medication

The frequency and percentage of subjects who took at least one dose of medication other than study drug (rovalpituzumab tesirine and dexamethasone) will be summarized by the anatomical therapeutic chemical (ATC) codes in the World Health Organization (WHO) Drug dictionary. Prior and concomitant medications will be summarized separately.

A similar summary will be prepared for prior medications.

There will be no statistical comparison for the prior and concomitant medications between treatment arms.

